### **2.3 Study Population**

Patients will be eligible for study participation as defined by following inclusion and exclusion criteria:

#### **Inclusion criteria**

1. Patient must be able to understand and communicate with the investigator and comply with the requirements of the study and must provide written, signed and dated informed consent form before any study assessment is performed.
2. Male or female patients  $\geq 18$  years of age.
3. Patients diagnosed with primary or secondary PGF after allo-HSCT defined as two or more cytopenias after day +30 post-transplant (re-tested in a peripheral blood analysis at screening):
  - Platelet count  $<20,000/\mu\text{L}$  (mandatory).
  - Absolute neutrophil count (ANC)  $<1,000/\mu\text{L}$ .
  - Hemoglobin  $< 100 \text{ g/L}$ .
4. Presence of donor chimerism  $>90\%$  in screening visit.
5. Karnofsky status  $\geq 90\%$  (Karnofsky assessment must be performed within 7 days prior to Day 1).

**Exclusion criteria****1. Pregnancy statements and contraception requirements:**

Pregnant or nursing (lactating) women, where pregnancy is defined as the state of a female after conception and until the termination of gestation, confirmed by a positive hCG laboratory test.

[figure not shown]
Women of child-bearing potential, defined as all women physiologically capable of becoming pregnant (or female partners of male patients), unless they are using highly effective methods of contraception during dosing and for 3 months after stopping medication. Highly effective contraception methods include:

- Total abstinence (when this is in line with the preferred and usual lifestyle of the subject. Periodic abstinence (e.g., calendar, ovulation, symptothermal, post-ovulation methods) and withdrawal are not acceptable methods of contraception.
- Female sterilization (have had surgical bilateral oophorectomy with or without hysterectomy), or tubal ligation at least six weeks before taking study treatment. In case of oophorectomy alone, only when the reproductive status of the woman has been confirmed by follow up hormone level assessment.
- Male sterilization (at least 6 months prior to screening). For female subjects on the study the vasectomized male partner should be the sole partner for that subject
- Use of oral, injected or implanted hormonal methods of contraception or placement of an intrauterine device (IUD) or intrauterine system (IUS), or other forms of hormonal contraception that have comparable efficacy (failure rate <1%), for example hormone vaginal ring or transdermal hormone contraception.

In case of use of oral contraception women should have been stable on the same pill for a minimum of 3 months before taking study treatment.

[figure not shown]
Sexually active males unless they use a condom during intercourse while taking the drug during treatment and for 3 months after stopping treatment and should not father a child in this period. A condom is required to be also used by vasectomized men as well as during intercourse with a male partner to prevent delivery of the drug via semen.

2. Evidence of active acute or chronic graft versus host disease (GVHD).
3. Evidence of any active malignancy.
4. Subjects who are human immune deficiency virus (HIV), hepatitis C virus (HCV), hepatitis B surface antigen (HBsAg) positive in screening visit.

5. Cytogenetic abnormality in chromosome 7 present before the allo-HSC.
6. Evidence of any clonal abnormality on cytogenetics (in bone marrow analysis).
  - A local post-transplant conventional cytogenetic assessment should be available within 8 weeks before Day 1.
  - If the cytogenetics is not valuable, i.e, it does not show metaphases, a FISH for MDS-related most frequent abnormalities including chromosome 7 is accepted.

As a consequence, patients with dry tap bone marrow aspiration are NOT eligible.
7. Evidence of bone marrow involvement or progression of the underlying disease assessed by the applicable methods in each case.
8. Evidence of thrombotic microangiopathy.
9. Evidence of possible causes of cytopenia other than PGF (active infections, myelotoxic drugs, hypersplenism...).
10. Prior use of any thrombopoietin receptor (TPO-R) agonists for PGF.
11. AST or ALT levels  $>3 \times$  ULN.
12. Creatinine level  $\geq 1.5 \times$  ULN.
13. Total bilirubin level  $\geq 1.5 \times$  ULN.
14. Previous thromboembolic event (other than line-related upper extremity thrombosis)
15. Hypersensitivity to eltrombopag or its components.
16. Clinically significant ECG abnormality history or current diagnosis of cardiac disease indicating significant risk of safety for subjects participating in the study such as uncontrolled or significant cardiac disease or impaired cardiac function including any of the following:
  - a). Corrected QTc  $> 450$  msec (male subjects),  $> 460$  msec (female subjects) using Fredericia correction (QTcF) on the screening ECG
  - b). Myocardial infarction
  - c). Uncontrolled congestive heart failure
  - d). Unstable angina
  - e). Congenital long QT syndrome.
17. Administration of an investigational drug within 30 days or 5 half-lives, whichever is longer, preceding the first dose of study treatment.
18. Patient with liver cirrhosis.

19. Risk factors for Torsade de Pointes including uncorrected hypokalemia or hypomagnesemia.
20. Subjects with any serious and/ or unstable pre-existing medical, psychiatric disorder or other conditions that could interfere with patient's safety, obtaining informed consent or compliance with the study procedures as per investigator discretion.

### **3 STATISTICAL METHODS**

Quantitative variables are described with measures of central tendency and dispersion: mean, median, SD, Q1, Q3, minimum and maximum).

Qualitative variables are described using absolute and relative frequencies (N, %). Two percentage columns are presented, total percentage (total %) and valid percentage (valid %), that is, the percentage over the sum of valid responses plus missing values and the percentage over the total of valid responses. When there are not missing values both of them are equal, and then only one will be show.

[figure not shown]
In the analysis of contingency tables as well as for the comparison of proportions and / or frequency distributions, the chi-square test (or Fisher's exact when appropriate) will be used.

For dependent samples, parametric (t-test paired) or non-parametric (Wilcoxon) statistical tests will be performed depending on the distribution of the sample.

The "time to event" variables (overall survival) will be analyzed using the Kaplan-Meier method.

These tests will be used in all bilateral cases and with a level of significance of 0.05. In cases where a p-value less than 0.05 appears, it refers to the existence of statistical significance.

Data will be analyzed using SPSS v22.0.

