10.4.2 Statistical hypothesis, model, and method of analysis

No hypotheses or models will be considered for these analyses and descriptive statistics will be provided; inferences to the target population (when applicable) will be made using interval estimation.

The proportion of patients who reach the overall response rate (partial and complete) by 16 weeks after the initiation of eltrombopag will be calculated and the corresponding 95% confidence interval (CI). This CI will be one-sided and will be constructed using the relationship between the sums of binomial probabilities and the F distribution described by Clopper and Pearson using the formulas proposed elsewhere (Fleiss JL, Levin B, Paik MC. Statistical Methods for Rates and Proportions. Third edition. John Wiley & Sons: New York, 2003, pp. 25):

$$P_L = \frac{x_0}{x_0 + (n - x_0 + 1)F_{2(n-x_0+1), 2x_0; \alpha}}$$

where $\alpha=0.05$, x_0 is the observed number of responders in the sample and n the sample size.

Descriptive statistics will also be provided between baseline and 16 weeks for blood cell counts (ANC and platelet) and hemoglobin levels, and appropriate paired exploratory tests will be done according to the type of distribution (parametric or not) to assess the statistical significance of the changes.

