10.5.1 Other efficacy objective(s)

- To determine the response in each haematological lineage separately, the absolute frequency and valid percentage of patients who have a response in the neutrophil, platelet, and Hb lineages separately after 16, 24 and 36 weeks of eltrombopag, will be presented with the 95% CI. Descriptive statistics will also be provided between baseline and weeks 16, 24 and 36 for ANC, platelets and hemoglobin levels, and the appropriate paired exploratory tests will be done according to the type of distribution (parametric or not) to assess the statistical significance of the changes.
- To evaluate the overall hematological response rate (partial and complete) at 24 and 36 weeks after the initiation of eltrombopag, the frequency and percentage distribution and the corresponding 95% CI will be provided. This CI will be constructed as for the primary efficacy endpoint. Descriptive statistics will also be provided between baseline and week 24 and week 36 for ANC, platelets count and hemoglobin levels, and the appropriate paired exploratory tests will be done according to the type of distribution (parametric or not) to assess the statistical significance of the changes.
- To evaluate transfusion independence, the percentage of patients who were previously transfusion-dependent and do no longer require a RBC or platelet transfusion before and after the first 16 weeks of treatment will be calculated along with the 95% CI. This CI will be constructed as for the primary efficacy endpoint. The period where patients did not receive any platelet or RBC transfusions during the treatment period and follow-up will also be analyzed.

- To evaluate the discontinuation or reduction of concomitant G-CSF and/or EPO therapy, the percentage of patients who discontinue or reduce by $\geq 50\%$ from baseline the use of concomitant G-CSF and/or EPO therapy will be calculated along with the 95% CI. This CI will be constructed as for the primary efficacy endpoint.
- Overall survival, defined as the duration from inclusion in the study to date of death (whatever the cause), will be estimated with the Kaplan-Meier curves method and two-sided 95% CI for the estimated median. All patients who discontinue from the study, regardless the reason of discontinuation, will be followed for survival for 24 and 36 weeks, unless they withdraw their consent, die or are lost-to follow-up, in which case will be censored at the last contact.

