**To determine the response in each hematological lineage separately.**

It will be calculated:

- Percentage of patients who have a partial response in the neutrophil lineage, defined as Absolute neutrophil count (ANC)  $\geq 1,000/\mu\text{L}$  (when pretreatment ANC was  $< 1,000/\mu\text{L}$ ) confirmed in two consecutive blood tests separated a minimum of 7 days.
- Percentage of patients who have a complete response in the neutrophil lineage, defined as Absolute neutrophil count (ANC)  $\geq 1,500/\mu\text{L}$  (when pretreatment ANC was  $< 1,000/\mu\text{L}$ ) confirmed in two consecutive blood tests separated a minimum of 7 days.
- Percentage of patients who have a response in the neutrophil lineage (partial or complete).
- Percentage of patients who have a partial response in the platelet lineage, defined as Platelet count  $\geq 20,000/\mu\text{L}$  (with platelet transfusion independence), confirmed in two consecutive blood tests separated a minimum of 7 days.
- Percentage of patients who have a complete response in the platelet lineage, defined as Platelet count  $\geq 100,000/\mu\text{L}$  (with platelet transfusion independence), confirmed in two consecutive blood tests separated a minimum of 7 days.

- Percentage of patients who have a response in the platelet lineage (partial or complete).
- Percentage of patients who have a partial response in the hemoglobin lineage, defined as Hemoglobin  $\geq 100\text{g/L}$  (when pretreatment Hb was  $<100\text{g/L}$ ) (with red blood cells (RBC) transfusion independence), confirmed in two consecutive blood tests separated a minimum of 7 days.
- Percentage of patients who have a complete response in the hemoglobin lineage, defined as Hemoglobin  $\geq 110\text{g/L}$  (when pretreatment Hb was  $<100\text{g/L}$ ), confirmed in two consecutive blood tests separated a minimum of 7 days.
- Percentage of patients who have a response in the hemoglobin lineage (partial or complete).

Responses in each hematological lineage separately will be determined at weeks 16, 20, 24, 30 and 36 after the initiation of eltrombopag.

In addition,

- To assess if there are statistical significance differences in ANC between baseline and week 24, it will be applied the appropriate paired test (T-test paired or Wilcoxon, depending the distribution of sample).

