**To evaluate the transfusion independence for red blood cells (RBC) and/or platelets after the initiation of eltrombopag.**

It will be calculated:

- The patient receive at least one transfusion before start treatment (No / Yes) (data in section “Supportive Care Record”).
- The patient receive at least one transfusion after start treatment and before week 16 (No / Yes) (data in section “Supportive Care Record”).
- The patient receive at least one transfusion after week 16 and before end treatment (No / Yes) (data in section “Supportive Care Record”).

In each of the studied moments, it will be shown the number of transfusions per patient. In addition, for total of transfusions, it will be shown the type of transfusion (Platelets / RBC).

It will be performed:

- Analysis of contingency tables between number of patients with transfusions before start treatment and before week 16, using chi-square or Fisher's exact test.
- Analysis of contingency tables between number of patients with transfusions before start treatment and after week 16, using chi-square or Fisher's exact test.

It will be calculated:

- The period of time where patients did not receive any platelet or RBC transfusions during the treatment period, calculated as the difference between the number of days in treatment and the number of days with transfusions.

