#### **10.5 Secondary objective 4**

##### **To evaluate the reduction and discontinuation of concomitant granulocyte colony-stimulating factor (G-CSF) and/or erythropoietin (EPO) therapy.**

It will be calculated:

- The patient receive EPO at start of treatment (No / Yes) (data in section "Supportive Care Record").
- The patient receive EPO in visit 6, visit 9, visit 11, visit 13, visit 15 and visit 16 (No / Yes) (data in section "Supportive Care Record").
- The patient reduce EPO at least 50% from start of treatment to visit 6, visit 9, visit 11, visit 13, visit 15 and visit 16 (No/ Yes) (data in section "Supportive Care Record").
- The patient receive G-CSF at start of treatment (No / Yes) (data in section "Supportive Care Record").
- The patient receive G-CSF in visit 6, visit 9, visit 11, visit 13, visit 15 and visit 16 (No / Yes) (data in section "Supportive Care Record").
- The patient reduce G-CSF at least 50% from start of treatment to visit 6, visit 9, visit 11, visit 13, visit 15 and visit 16 (No / Yes) (data in section "Supportive Care Record").

It will be realized:

- Analysis of contingency tables between number of patients who receive EPO at start of treatment and in visit 6, visit 9, visit 11, visit 13, visit 15 and visit 16, using chi-square or Fisher's exact test.
- Analysis of contingency tables between number of patients who receive G-CSF at start of treatment and in visit 6, visit 9, visit 11, visit 13, visit 15 and visit 16, using chi-square or Fisher's exact test.

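### The SAP reads every two-sided p<0.05 as statistical significance across 20 unadjusted secondary tests, with no exploratory label on any of them

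*SAP*

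**What the plan says.** SAP section 3 fixes the level for all tests: "These tests will be used in all bilateral cases and with a level of significance of 0.05". The next sentence says how to read the result: "In cases where a p-value less than 0.05 appears, it refers to the existence of statistical significance".

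The SAP then names these tests, all under secondary objectives:

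- **SAP 10.2:** paired t or Wilcoxon tests of ANC, platelets and hemoglobin, each at weeks 24 and 36. The first reads "To assess if there are statistical significance differences in ANC between baseline and week 24, it will be applied the appropriate paired test".
- **SAP 10.4:** two chi-square or Fisher tests on transfusions, before treatment against before week 16 and against after week 16 ("Analysis of contingency tables between number of patients with transfusions before start treatment and before week 16").
- **SAP 10.5:** chi-square or Fisher tests for EPO and for G-CSF, start of treatment against each of six visits ("Analysis of contingency tables between number of patients who receive EPO at start of treatment and in visit 6, visit 9" and four later visits, then the same for G-CSF).

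Protocol 10.4.2, under the primary objective, states: "No hypotheses or models will be considered for these analyses and descriptive statistics will be provided". It adds that inference to the target population will be by interval estimation. For the blood counts, protocol 10.5.1 says "the appropriate paired exploratory tests will be done according to the type of distribution"; the same sentence gives their purpose as judging whether the changes are statistically significant. For transfusion independence and growth-factor reduction, protocol 10.5.1 plans percentages with 95% confidence intervals and no tests. Protocol 10.8 marks power for key secondary variables as not applicable.

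**The concern.** The SAP does more than omit a multiplicity statement. It gives a positive reading rule, and applied literally that rule lets any one of 20 nominal results be reported as a statistically significant finding on a secondary objective. No visit is named as decisive for EPO or G-CSF, so the most favourable of six could carry the message. The trial is single-arm, plans 33 patients and sets up no hypothesis for any secondary endpoint.

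The protocol frames these analyses more cautiously than the SAP does. For the 6 paired tests the SAP keeps the reference to significance and leaves out the word exploratory. The 14 contingency tests never had a label, because the protocol did not plan them.

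This is separate from whether chi-square or Fisher suits before/after data on the same patients. Replacing them with paired tests would still leave an unlabelled family of 20.

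**Working it through.** **1. The plan's own figure.** Neither document states a family-wise error rate. The only design figure is the one-sided 95% Clopper-Pearson lower limit of 30.1% for 45% of 33 (protocol 10.7). With x = 0.45 × 33 = 14.85, the 5th percentile of Beta(14.85, 33 − 14.85 + 1) is 30.08%, so it reproduces. It involves none of the tests below.

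**2. Count.**

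- SAP 10.2: 3 lineages × 2 weeks = 6
- SAP 10.4: 2
- SAP 10.5: 2 agents × 6 visits = 12
- Total: 6 + 2 + 12 = 20

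Protocol 10.4.2 and 10.5.1 also plan paired count tests at week 16. SAP 10.2 does not list them, so they are not counted.

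**3. Chance of at least one p<0.05 when nothing changes.** The level is 0.05 two-sided (SAP section 3), which is 0.025 in the direction of benefit. The correlation between tests is not in the documents, so it is an assumption shown as a range.

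Independent tests:

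- Either direction, k = 20: 1 − 0.95^20 = 0.642
- Benefit only, k = 20: 1 − 0.975^20 = 0.397
- Either direction, k = 6: 1 − 0.95^6 = 0.265
- Benefit only, k = 6: 1 − 0.975^6 = 0.141

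Common correlation ρ between normal test statistics, with u standard normal and c = 1.96:

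- Either direction: 1 − E{[Φ((c − √ρ·u)/√(1−ρ)) − Φ((−c − √ρ·u)/√(1−ρ))]^k}
- Benefit only: 1 − E{[Φ((c − √ρ·u)/√(1−ρ))]^k}

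| Tests | Direction | ρ = 0 | ρ = 0.5 | ρ = 0.9 |
|---|---|---|---|---|
| All 20 | either | 64% | 42% | 16% |
| All 20 | benefit | 40% | 21% | 8% |
| 6 paired | either | 27% | 21% | 11% |
| 6 paired | benefit | 14% | 10% | 5% |

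**4. Does every test run at nominal size?** No. Fisher's test on small counts is discrete, and treating before and after as independent samples ignores the pairing. A patient-level simulation used paired t-tests for the 6 and Fisher's test for the 14. It assumed n = 33 at every visit, no change over time, independent endpoints, and use of 80% (transfusion), 30% (EPO) and 30% (G-CSF).

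| Within-patient correlation | 14 contingency, either | 6 paired, either | All 20, either | All 20, benefit |
|---|---|---|---|---|
| 0 | 25.5% | 23.7% | 43.0% | 24.6% |
| 0.3 | 15.3% | 23.0% | 34.6% | 18.6% |
| 0.6 | 5.1% | 24.5% | 28.4% | 14.7% |
| 0.8 | 0.9% | 24.6% | 25.4% | 13.5% |

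As within-patient correlation rises, the contingency tests add almost nothing and the 6 paired tests account for nearly all of the excess. The figures in step 3 for all 20 tests are therefore upper figures for a given correlation between tests.

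**The case against.** The strongest reply is that this is ordinary reporting language in a pilot, single-arm phase II study. The primary result is a single confidence limit, no secondary p-value triggers a decision, and the protocol itself says the paired tests assess statistical significance. The SAP does not revoke the word exploratory; it is silent on it. Most of this stands, and it limits the point to labelling. It does not remove the point, because the protocol attaches exploratory to those tests in the same sentence, and the SAP's reading rule also covers 14 tests for which the protocol says nothing.

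A reader might infer three stronger things that the documents do not support:

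- **That the SAP strips an exploratory label from all 20 tests.** The label existed for 6 and never existed for 14.
- **That a false benefit has a 64% or 42% chance.** Those rates count either direction. In the benefit direction they are 40% and 21%, falling to 8% at a correlation of 0.9. If the EPO and G-CSF tables cross use at baseline with use at a later visit, they test association, and a small p-value would not indicate benefit at all.
- **That formal family-wise control is required.** Holm across 20 tests of mixed and partly doubtful type is a debatable trade-off for secondaries that decide nothing.

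The no-change model is also artificial for the paired tests. Entry requires low counts, and patients without a response at week 16 leave the study (protocol 6.1.2), so week 24 and 36 pairs come largely from patients whose counts had already risen. Multiplicity adjustment would not cure that selection. It is a further reason not to present a nominal p<0.05 as an established drug effect.

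**Conclusion.** The point holds as a labelling fault in the SAP that should be corrected. SAP section 3 tells the analyst to read any of 20 unadjusted secondary p-values below 0.05 as statistical significance, whereas the protocol rests on interval estimation and calls the paired tests exploratory.

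If all tests ran at nominal size with no true change, the chance of at least one such result would be 16% to 64% in either direction and 8% to 40% in the benefit direction, over assumed correlations from 0.9 down to 0. The benefit figures are about 3 to 16 times the nominal 2.5% per test. For the 6 paired tests alone the ranges are 11% to 27% and 5% to 14%.

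These sizes rest on an assumed common correlation and on nominal test size, which the 14 contingency tests do not reach when within-patient correlation is high. The absence of an exploratory label is judged on the visible SAP text; part of the SAP is redacted.

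A reader might infer that the trial's main conclusion is at risk. It is not: the primary endpoint is analysed by a confidence limit and is not among these tests.

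**What to change.** In SAP section 3, replace the sentence that equates p<0.05 with significance by:

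> *All p-values in sections 10.2, 10.4 and 10.5 are exploratory, two-sided and nominal (20 tests, unadjusted for multiplicity), and will not be presented as confirmatory evidence of an eltrombopag effect. Secondary confidence intervals are reported for estimation only.*

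Carry the label into the footnotes of the tables for those three sections, and reword SAP 10.2, where "To assess if there are statistical significance differences in ANC between baseline and week 24" and its five counterparts should become exploratory comparisons. The wording leaves in place the secondary 95% intervals that protocol 10.5.1 plans.

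The cost is one SAP sentence, the footnotes and the rewording of 10.2. No data, patients or analyses change. The downside is that nominal p<0.05 results on secondary endpoints can no longer be reported as established significant effects.
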